## **8. STUDY ASSESSMENTS**

The procedures and assessments that will be conducted during this study are described in this section and summarized in the Schedule of Assessments ([Table 4](#)). Detailed instructions regarding all laboratory procedures, including collection and handling of samples, will be included in the study Laboratory Manual provided by the Sponsor or its designee.

Written informed consent must be granted by each subject prior to the initiation of any study procedure or assessment.

Study visits will occur daily for 5 days (inpatient), at  $7 \pm 1$  day after Dose #1 (outpatient), and at  $28 \pm 3$  days after Dose #1 (outpatient). Subjects will be kept in-house until after the last blood sample is taken on Day 5 and asked to return on Days 7 and 28.

**Table 4: Schedule of Assessments**

	Outpatient	Inpatient	Inpatient	Inpatient	Inpatient	Discharge	Outpatient	Outpatient
Visit	Screening	Baseline/ Randomization /Treatment	Treatment/Follow-Up Days					EOS Visit
Day	-6 weeks to 0	1	2	3	4	5	7 ±1	28 ± 3
Informed consent	X							
Eligibility assessment	X							
Demographics	X							
Medical history	X							
Blood or urine pregnancy test a	X b							X
Physical exam (incl. height and weight)	X							
Vital signs c	X	X	X	X	X	X	X	
Blood/urine for safety laboratory analyses d	X b						X	X
Adverse events e		X	X	X	X	X	X	X
Review of Systems/Symptoms e	X	X	X	X	X	X	X	X
Study drug administration f		X/X (0 and 12 hours)	X (36 hours)	X (60 hours)	X (84 hours)			
Blood sampling for pGSN levels g		X (Dose #1)			X (Dose #5)	X (24 hours after Dose #5)	X	X

	Outpatient	Inpatient	Inpatient	Inpatient	Inpatient	Inpatient	Discharge	Outpatient	Outpatient
Visit	Screening	Baseline/ Randomization /Treatment	Treatment/Follow-Up Days						EOS Visit
Day	-6 weeks to 0	1	2	3	4	5	7 ± 1	28 ± 3	
Anti-rhu-pGSN antibody sampling		X							X
Concomitant medications	X	X	X	X	X	X	X	X	

Abbreviations: AEs=adverse events; ALT=alanine aminotransferase; aPTT=activated partial thromboplastin time; AST=aspartate aminotransferase; CBC=complete blood count; CPK=creatine phosphokinase; EOS=end of study; PK=pharmacokinetic; PT=prothrombin time

a Perform a serum or urine pregnancy test for female subjects unless they have had a hysterectomy.

b If performed more than 36 hours before initiation of study drug, the test must be repeated within this time frame.

c Record blood pressure, oral temperature, respiration rate, and heart rate. To be measured during infusions at the following time points: pre-infusion, every 15 minutes after the start of infusion, at the end of infusion, and 30 minutes after the end of infusion.

d Safety labs include collection of blood for a CBC, PT, aPTT, creatinine, bilirubin, alkaline phosphatase, CPK, AST, and ALT levels and collection of urine for drug screening (e.g., amphetamines, benzodiazepines, cannabinoids, cocaine, and opiates) and urinalysis (dipstick: glucose, protein, red blood cells, white blood cells).

e Subjects will be interviewed to assess any possible AEs daily for 5 days, at 7 ± 1 day after Dose #1, and at 28 ± 3 days after Dose #1 (EOS Visit). Interviews can be done in person or by phone as mutually agreed by the Investigator and subject, but the EOS Visit should be done in person if possible so blood specimens can be collected.

f Study drug will be administered by IV infusion at time 0 (Day 1), 12 hours (Day 1), 36 hours (Day 2), 60 hours (Day 3), and 84 hours (Day 4). Dose 1 will be at time 0, and a window of ±2 hours will be allowed around dosing times for the 2nd and 3rd doses, and ±4 hours for the last 2 doses. Subjects are to be monitored for administration site reactions during an infusion and for 1 hour after its completion.

g Approximately 5 mL volume of blood will be drawn for measurement of pGSN levels on Day 1 within 30 minutes predose, and at 15 minutes and 1, 2, 4, 8, and 12 hours after Dose #1 and on Days 4 and 5 within 30 minutes predose, and at 15 minutes and 1, 2, 4, 8, 12, and 24 hours after Dose #5. Plasma will be obtained after centrifugation and promptly frozen at -20°C for assay in the central lab. A window of ±15 minutes will be allowed around the scheduled times except for the samples collected at 15 minutes postdose which have a window of ±5 minutes. A single sample will be collected anytime on Days 7 and 28.

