**Endpoints/Outcomes:**

**Primary**

- Incidence and severity of clinical and laboratory AEs regardless of causality graded according to the *Toxicity Grading Scale for Healthy Adult and Adolescent Volunteers Enrolled in Preventive Vaccine Clinical Trials*

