Two subjects experienced SAEs: 1 SAE was reported in 1 subject who received a single dose of rhu-pGSN, and 2 SAEs were reported in 1 subject who received placebo in the multiple ascending dose phase. One subject who received a single dose of rhu-pGSN had an SAE of pneumonia (Grade 5, not related) after being withdrawn from the study; and 1 subject who received placebo had SAEs of pneumonia (Grade 4, not related) and pulmonary embolism (Grade 5, not related).

Pharmacokinetic analyses showed that the median rhu-pGSN half-life exceeded 17 hours with all dosing regimens. Overall, rhu-pGSN was well tolerated in patients admitted to non-ICU beds with CAP.

**Study BTI-202** was a Phase 2 randomized, double-blind, placebo-controlled study to evaluate the efficacy and safety of rhu-pGSN added to SOC for the treatment of subjects hospitalized with severe COVID-19 pneumonia (NCT04358406) (DiNubile et al., 2022). The study was conducted

in Spain and Romania. Sixty-four subjects with severe COVID-19 pneumonia were randomized 1:1 to receive rhu-pGSN or placebo intravenously in addition to SOC. Standard of care was left to the judgment of the caregivers without restrictions. Three doses of rhu-pGSN 12 mg/kg based on actual body weight were administered at 0, 12, and 36 hours. Of the 61 treated subjects, 54 completed the study, 4 died, and 3 were lost to follow-up. No subject discontinued due to an AE. The primary efficacy endpoint, the proportion of subjects alive without respiratory, hemodynamic, or renal support on Day 14, did not differ between treatment arms: 25 of 30 rhu-pGSN recipients (83.3%) and 27 of 31 placebo recipients (87.1%). Adverse events occurred with similar frequencies in both treatment groups. Most AEs were mild to moderate in severity and related to COVID-19 pneumonia. Serious adverse events were numerically fewer in the rhu-pGSN group than placebo group and all were assessed as unrelated to study drug. No pattern of AEs was discernable in either treatment arm. Two subjects in each group died during the 90-day study, but no deaths were attributable to study drug.

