### 5.2. Safety Review Committee

The safety data will be reviewed by a Safety Review Committee (SRC) comprised of at least 1 expert clinician, the Medical Monitor at the contract research organization, and the Sponsor's Chief Medical Officer.

Adverse events (AEs) will be categorized as "serious" according to the judgement of the site investigator as to whether the definition of SAE (section 9.1.2) is met and then reviewed and adjudicated by the SRC. The "severity" of an AE will be graded according to the Toxicity Grading Scale for Healthy Adult and Adolescent Volunteers Enrolled in Preventive Vaccine Clinical Trials. An individual patient will be discontinued permanently from study treatment if they experience any serious adverse event (SAE) or a severity Grade 3 or greater AE (including infusion reactions). Further study treatment and enrollment will be paused pending review by the SRC if there are two Grade 3 AEs, one Grade 4 AE, or one SAE. The study will only be resumed if the SRC unanimously judges the AEs as unrelated to study treatment and procedures after consultation with regulatory and outside experts as needed.

The SRC will review safety data (including lab tests) through the Day 7 visit for each dosing arm to determine if it is safe to initiate the next cohort according to the safety criteria for stopping doses ([Section 5.3](#)).

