### **8.1.5. Laboratory Assessments**

Where indicated, handling and shipping clinical laboratory samples to a central laboratory will be outlined in the Laboratory Manual. If a laboratory screening assessment is performed more than 36 hours before initiation of study drug, the test must be repeated within this time frame.

Blood will be collected at the time points specified in [Table 4](#) for safety laboratory evaluations including complete blood count [CBC], prothrombin time (PT), activated partial thromboplastin time (aPTT), creatinine, bilirubin, alkaline phosphatase, creatine phosphokinase [CPK], aspartate aminotransferase [AST], and alanine aminotransferase [ALT] levels.

In addition, urine will be collected at the time points specified in [Table 4](#) for drug screening (e.g., amphetamines, benzodiazepines, cannabinoids, cocaine, and opiates) and urinalysis (dipstick: glucose, protein, red blood cells, white blood cells).

Abnormal laboratory test results considered clinically significant by the Investigator or that require treatment should be reported as AEs in the eCRF.

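### No safety laboratory panel is scheduled between Dose #1 and the Day 7 visit, so transient, symptom-free laboratory changes during dosing can be missed

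*Combined protocol and SAP*

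**What the plan says.** The Table 4 row "Blood/urine for safety laboratory analyses" carries marks at screening, Day 7 ±1 and Day 28 ±3. The cells for Days 1 to 5 are empty, while the rows for vital signs, adverse events and study drug are filled in for the dosing days. Footnote b covers the predose sample: "If performed more than 36 hours before initiation of study drug, the test must be repeated within this time frame". Section 8.1.5 sets no further times: "Blood will be collected at the time points specified in" Table 4.

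Doses are given at 0, 12, 36, 60 and 84 h, with a window of ±2 h for the second and third doses "and ±4 hours for the last 2 doses" (Table 4, footnote f). Section 8 and footnote e place the Day 7 visit at 7 ±1 days after Dose #1. Blood is already drawn in-house for pGSN on Day 1, before and after Dose #5 on Day 4, and 24 h after Dose #5 on Day 5 (footnote g).

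Laboratory results have three uses in the plan:
- The synopsis defines the primary endpoint as "Incidence and severity of clinical and laboratory AEs regardless of causality graded according to the" the named toxicity scale. Section 4.2.1 omits the word laboratory, but Section 9.6 grades laboratory adverse events.
- Sections 5.2 and 5.3 discontinue a subject for any Grade 3 or greater event, and pause the study for two Grade 3 events or one Grade 4 event.
- Section 5.2 bases escalation on laboratory data: "The SRC will review safety data (including lab tests) through the Day 7 visit for each dosing arm".

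**The concern.** The trial is meant to show whether five doses are tolerated, and laboratory findings are one of its measures. Interviews, symptom review and vital signs cover the dosing days; laboratory tests do not. Changes in CPK, transaminases, creatinine, PT/aPTT or blood counts can occur without symptoms, so the daily interviews are not a substitute. A change that appears during dosing and resolves by Day 7 would leave no trace in the scheduled data.

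Two decisions are affected. When the committee decides on escalation, it has one scheduled post-dose panel per subject, taken days after the last dose. And no scheduled laboratory result can bear on the discontinuation or pausing rules while the subject concerned is still being dosed. The regimen is also longer than before: Section 10.2 says the earlier studies in hospitalized patients gave three doses, against five here.

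**Working it through.** The plan states no interval between Dose #5 and the laboratory draws. Its only design calculation is Table 5, which is reproduced first and used again in step 5.

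1. **Table 5.** The chance of at least one event in n subjects at true rate p is 1 − (1 − p)^n. For n = 24, p = 0.10: 1 − 0.90^24 = 0.920. For n = 6, p = 0.32: 1 − 0.68^6 = 0.901. The other rows give 0.900 (n = 8, 25%), 0.908 (n = 12, 18%) and 0.918 (n = 18, 13%). The table reproduces at about 90% or slightly better. It assumes that every event that occurs is observed.

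2. **Time from Dose #5 to the panels.** Dose #5 is at 84 ± 4 h.
   - Day 7 as 7 ± 1 days after Dose #1 (168 ± 24 h): earliest 144 − 88 = 56 h, nominal 168 − 84 = 84 h, latest 192 − 80 = 112 h.
   - Day 7 counted with 0 h as Day 1, as in the Table 4 columns (144 ± 24 h): 120 − 88 = 32 h, 144 − 84 = 60 h, 168 − 80 = 88 h.
   - Day 28 as 28 ± 3 days after Dose #1 (672 ± 72 h): 600 − 88 = 512 h to 744 − 80 = 664 h.

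3. **Level remaining.** Assume that, after the last dose, the above-baseline level falls as 2^(−t/T). Section 3.4.2 reports, in patients with community-acquired pneumonia, that "the median rhu-pGSN half-life exceeded 17 hours with all dosing regimens", so T = 17 h is a lower bound. T = 24 h and 36 h are assumptions. They lie in the direction that Section 3.5 points to, since it expects faster consumption in sick patients than in healthy subjects. Percent of the post-Dose #5 peak remaining:

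| T | 24 h (Day 5 draw) | 32 h | 56 h | 84 h | 88 h | 112 h |
|---|---|---|---|---|---|---|
| 17 h | 37.6 | 27.1 | 10.2 | 3.3 | 2.8 | 1.0 |
| 24 h (assumed) | 50.0 | 39.7 | 19.8 | 8.8 | 7.9 | 3.9 |
| 36 h (assumed) | 63.0 | 54.0 | 34.0 | 19.8 | 18.4 | 11.6 |

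4. **Exposure already past.** With equal doses at d = 0, 12, 36, 60 and 84 h, the share of total above-baseline AUC accrued by 140 h (56 h after Dose #5) is 1 minus the mean of 2^(−(140 − d)/T).
   - T = 17 h: 1 − (0.0033 + 0.0054 + 0.0144 + 0.0383 + 0.1019)/5 = 1 − 0.1633/5 = 0.967.
   - T = 36 h: 1 − (0.0675 + 0.0850 + 0.1350 + 0.2143 + 0.3402)/5 = 1 − 0.8420/5 = 0.832.

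5. **Effect on Table 5.** Suppose a share s of subjects with a transient laboratory event still show it on Day 7. The documents give no value for s. Detection becomes 1 − (1 − ps)^n.
   - n = 24, p = 0.10: 92% at s = 1, 71% at s = 0.5, 46% at s = 0.25.
   - n = 6, p = 0.32: 90%, 65% and 39%.

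6. **Level at the draws already scheduled.** At 24 h after Dose #5 it is 38% of peak (T = 17 h) to 63% (T = 36 h). Just before Dose #5, in units of one dose's increment, the first four doses leave S = sum of 2^(−(84 − d)/T), and the peak after Dose #5 is 1 + S.
   - T = 17 h: S = 0.033 + 0.053 + 0.141 + 0.376 = 0.603, and 0.603/1.603 = 38%.
   - T = 36 h: S = 0.198 + 0.250 + 0.397 + 0.630 = 1.475, and 1.475/2.475 = 60%.

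**The case against.** Persistent or late-appearing changes can still be seen on Day 7 or Day 28. Unscheduled tests are not prohibited. A change that is part of a clinical illness may be caught by the daily interviews or vital signs. Under Sections 8.1.5 and 9.6, an isolated abnormality becomes an adverse event only if it is treated or judged clinically significant, so some transient shifts would not count even if sampled. Section 3.4.1 reports no adverse clinical-pathology effects in repeat-dose IV animal studies, and Section 3.5 reports human dosing up to 24 mg/kg for three days without a distinctive signal. Nothing in the documents shows that important changes would resolve by Day 7.

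All of this stands, and it limits the loss mainly to transient changes without symptoms. It does not close the gap: unscheduled tests need something to prompt them, so they give no systematic record to set beside placebo.

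A reader might also infer that the laboratory data come only after washout. The documents do not support that. The 17 h figure is a lower bound from patients, and at an assumed 36 h up to 34% of the peak remains at 56 h, or 54% at 32 h on the other Day 7 reading. Nor do they support the inference that half of the primary endpoint goes unmeasured: the synopsis names laboratory events without giving them a weight, Section 4.2.1 does not name them, and Day 7 and Day 28 panels are taken.

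**Conclusion.** The gap is certain from Table 4: in all 32 subjects, no safety panel is scheduled between Dose #1 and the Day 7 visit. That visit falls 56-112 h after Dose #5 on the stated definition, or 32-88 h with 0 h counted as Day 1. Under either reading the dosing period and the post-Dose #5 peak are unsampled. About 10% to 1% of the peak remains at 56-112 h if the half-life is 17 h, and 34% to 12% if it is 36 h.

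The consequence is narrower than the gap: transient, symptom-free changes that resolve by Day 7 would be missed, and scheduled laboratory results cannot inform the Grade 3/4 rules during a subject's own dosing. How often this would matter cannot be determined from the documents. The detection figures in step 5 rest on assumed values of s, and the exposure figures on single-exponential decay. The change is worth making because it is cheap, not because harm has been shown.

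**What to change.** Amend the safety-laboratory row of Table 4 to add the blood panel and dipstick urinalysis at two pGSN draws that already exist:
- **Day 4, before Dose #5.** This is the only one of the two that gives a sample before dosing is complete. It can inform the rules ahead of Dose #5 only if results return in time, and the documents give no turnaround, so the protocol should state one.
- **Day 5, 24 h after Dose #5, before discharge.** This follows every dose, so it cannot inform the rules during dosing, but it samples much nearer the peak than Day 7 does.

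Split footnote d so that the urine drug screen, now bundled into the same row, is not repeated. Include the new results in the Day 7 committee review and in the Section 10.4.1 laboratory summaries. In the same amendment, reconcile the two ways of counting Day 7, and align the primary endpoint wording in the synopsis and Section 4.2.1.

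Cost: one or two extra panels per subject (32 × 1 = 32 to 32 × 2 = 64), a few mL more blood at existing venipunctures, a urine sample each time, and some incidental abnormalities to adjudicate. No new visit is needed, and dosing and the stopping criteria are unchanged.

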## **8.1. Safety Assessments**

Prior to screening, all subjects must provide informed consent for study participation, per [Section 12.5](#). The following assessments will be performed according to the time points in the Schedule of Assessments ([Table 4](#)).

### **8.1.1. Pregnancy Test**

Unless they have had a hysterectomy, female subjects are required to have a negative serum or urine pregnancy test at screening to participate in the study. If the screening test is performed more than 36 hours before initiation of study drug, the test must be repeated within this time frame.

### **8.1.2. Demographic/Medical History**

A review of demographic parameters, including age, gender, race, and ethnicity will be performed at screening.

Past and present medical history will be recorded. Any ongoing condition or signs and symptoms observed prior to the initiation of study treatment should be recorded as medical history.

### **8.1.3. Vital Signs**

Vital signs will include blood pressure, oral temperature, respiration rate, and heart rate, as well as pulse oximetry. Vitals signs will be measured during infusions at the following time points: pre-infusion, every 15 minutes after the start of infusion, at the end of infusion, and 30 minutes after the end of infusion. Significant findings noticed after the start of study drug that meet the definition of an AE must be recorded in the eCRF.

### **8.1.4. Physical Examination**

All physical examinations, including measurement of body height and weight for calculation of BMI, will be performed by a study physician or designee. Height need only be measured at the screening examination. The initial body weight measured at enrollment will be used to calculate rhu-pGSN dosing for all doses (so that an individual subject will always receive the same dose). The physical examination includes skin, head, ears, eyes, nose, throat, heart, lungs, abdomen, and neurologic system. Additional examination may be performed as found relevant by the Investigator.

### **8.1.5. Laboratory Assessments**

Where indicated, handling and shipping clinical laboratory samples to a central laboratory will be outlined in the Laboratory Manual. If a laboratory screening assessment is performed more than 36 hours before initiation of study drug, the test must be repeated within this time frame.

Blood will be collected at the time points specified in [Table 4](#) for safety laboratory evaluations including complete blood count [CBC], prothrombin time (PT), activated partial thromboplastin time (aPTT), creatinine, bilirubin, alkaline phosphatase, creatine phosphokinase [CPK], aspartate aminotransferase [AST], and alanine aminotransferase [ALT] levels.

In addition, urine will be collected at the time points specified in [Table 4](#) for drug screening (e.g., amphetamines, benzodiazepines, cannabinoids, cocaine, and opiates) and urinalysis (dipstick: glucose, protein, red blood cells, white blood cells).

Abnormal laboratory test results considered clinically significant by the Investigator or that require treatment should be reported as AEs in the eCRF.

## **8.2. Measurement of pGSN Levels and Pharmacokinetic Assessments**

As indicated in [Table 4](#), approximately 5 mL volume of blood will be drawn for measurement of pGSN levels on Day 1 within 30 minutes predose, and at 15 minutes and 1, 2, 4, 8, and 12 hours after Dose #1 and on Days 4 and 5 within 30 minutes predose, and at 15 minutes postdose, and 1, 2, 4, 8, 12, and 24 hours after Dose #5. A window of  $\pm 15$  minutes will be allowed around the scheduled times except for the samples collected at 15 minutes postdose which have a window of  $\pm 5$  minutes. A single sample will be collected anytime on Days 7 and 28.

Plasma will be obtained after centrifugation and promptly frozen at  $-20^{\circ}\text{C}$  for assay in the central lab for analysis of pGSN concentrations. The concentration-time data will be used for the determination of PK parameters: maximum concentration ( $C_{\max}$ ), time to maximum concentration ( $T_{\max}$ ), terminal half-life ( $T_{1/2}$ ), area under the curve from time zero to 8 hours ( $\text{AUC}_{0-8}$ ), area under the curve from time zero to 12 hours ( $\text{AUC}_{0-12}$ ), and additionally after Dose #5, area under the curve from time zero to 24 hours ( $\text{AUC}_{0-24}$ ) and time zero to infinity ( $\text{AUC}_{\text{inf}}$ ).

## **9. ADVERSE EVENT MANAGEMENT**

### **9.1. Definition of Adverse Events**

#### **9.1.1. Adverse Event (AE)**

An AE is the development of an undesirable medical condition or the worsening of a pre-existing medical condition following or during exposure to a pharmaceutical product, whether or not considered causally related to the product.

#### **9.1.2. Serious Adverse Event (SAE)**

A serious adverse event (SAE) is an AE occurring during any study phase (i.e., baseline, treatment, or follow-up), and at any dose of the investigational product, comparator, or placebo, that fulfills one or more of the following:

- Results in death
- It is immediately life-threatening
- It requires in-patient hospitalization or prolongation of existing hospitalization
- It results in persistent or significant disability or incapacity
- Results in a congenital abnormality or birth defect
- It is an important medical event that may jeopardize the subject or may require medical intervention to prevent one of the outcomes listed above.

All SAEs that occur after a subject has signed the consent form, including before or during treatment and within 28 days following the cessation of treatment, whether or not judged to be related to the study, must be recorded on forms provided by the Sponsor.

